9. Subject is on a stable dosage regimen of 1 to 3 AEDs. The daily dosage regimen of concomitant AED therapy must be kept constant for a period of at least 1 week prior to Screening. Vagal nerve stimulation is not counted as medical therapy; however, VNS settings must be kept constant for a period of at least 1 week prior to Screening.
10. Subject is an acceptable candidate for venipuncture.

*Clinical Study Protocol, Section 4.3.2 (Exclusion criteria). Original text:*

Subjects are not permitted to enroll in the study if any of the following criteria are met:

1. Subject is receiving any investigational drugs or using any experimental devices in addition to LCM.
2. Subject meets the withdrawal criteria for the primary study (with the exception of subjects who discontinued due to a dose reduction or status epilepticus), or is experiencing an ongoing serious AE (SAE).
3. Subject has a lifetime history of suicide attempt (including an active attempt, interrupted attempt, or aborted attempt), or has suicidal ideation in the past 6 months as indicated by a positive response (“Yes”) to either Question 4 or Question 5 of the Columbia-Suicide Severity Rating Scale (C-SSRS) at Screening.

*Was revised as follows:*

Subjects are not permitted to enroll in the study if any of the following criteria are met:

1. Subject is receiving any investigational drugs or using any experimental devices in addition to LCM.
3. Subject has a lifetime history of suicide attempt (including an active attempt, interrupted attempt, or aborted attempt), or has suicidal ideation in the past 6 months as indicated by a positive response (“Yes”) to either Question 4 or Question 5 of the Columbia-Suicide Severity Rating Scale (C-SSRS) at Screening.

Subjects who have participated in SP847 or other LCM pediatric clinical studies in epilepsy are not permitted to enroll in the study if any of the following criteria are met:

2. Subject meets the withdrawal criteria for the primary study (with the exception of subjects who discontinued due to a dose reduction or status epilepticus), or is experiencing an ongoing serious AE (SAE).

Subjects who enroll directly into SP848 without previous participation in a LCM clinical study are not permitted to enroll in the study if any of the following criteria are met:

4. Subject has ever received LCM.

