5. Subject has any medical or psychiatric condition that, in the opinion of the investigator, could jeopardize or would compromise the subject’s ability to participate in this study.
6. Subject has a medical condition that could reasonably be expected to interfere with drug absorption, distribution, metabolism, or excretion.
7. Subject has a known hypersensitivity to any component of the investigational medicinal product.
8. Subject is a female of childbearing potential and does not practice an acceptable method of contraception for the duration of the study.

- Medically acceptable contraceptive method includes oral or depot contraceptive treatment with at least 30 $\mu$ g ethinylestradiol per intake (or 50 $\mu$ g if associated with carbamazepine [or other strong enzyme inducers, eg, phenobarbital, primidone, oxcarbazepine]) which must be used in conjunction with a barrier method. Sexual abstinence is also an acceptable method of contraception.
- The subject must understand the consequences and potential risks of inadequately protected sexual activity, be educated about and understand the proper use of contraceptive methods, and undertake to inform the investigator of any potential change in status. Females of childbearing potential must have a negative pregnancy test at the Screening Visit.

9. Subject has an alanine aminotransferase (ALT), aspartate aminotransferase (AST), or total bilirubin level greater than or equal to 2 times the upper limit of normal (ULN), or creatinine clearance less than 50mL/min.
10. Subject has a clinically relevant ECG abnormality, in the opinion of the principal investigator (ie, second or third degree heart block at rest or a QT prolongation greater than 450ms).
11. Subject has hemodynamically significant heart disease (eg, heart failure).
12. Subject has an arrhythmic heart condition requiring medical therapy.
13. Subject has a known history of severe anaphylactic reaction or serious blood dyscrasias.
14. Subject has nonepileptic events, including psychogenic seizures, that could be confused with seizures. If both epileptic and nonepileptic events are present, epileptic events must be distinguished from nonepileptic phenomena.
15. Subject has a history of primary generalized epilepsy.

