- 12-lead ECG (2 interpretable recordings approximately 20 to 30 minutes apart prior to vital signs assessment and collection of blood sample)
- Vital signs assessment (blood pressure and pulse)
- Body weight assessment
- Height assessment
- Blood sample for clinical chemistry, hematology, and endocrinology
- Urine sample for urinalysis
- Serum pregnancy test for female subjects of childbearing potential
- Tanner Stage assessment (if applicable)
- Clinical Global Impression of Change
- Caregiver Global Impression of Change
- C-SSRS
- Achenbach CBCL to be completed by the parent(s)/legal representative(s) (CBCL/1½-5 for children from 18 months to 5 years 11 months and CBCL/6-18 for children 6 years and older)
- Bayley-III scales for children <18 months of age enrolled in English-speaking countries
- Adverse event reporting
- Dispense subject diary

The subject will be scheduled to return for a clinic visit (TV) less than 14 days from the last Screening Visit assessment(s).

*Clinical Study Protocol, Section 5.2 (Titration Visit[s] [TV1, TV2, TV3, TV4, TV5, TV6]) was newly added as follows and subsequent section numbers were adjusted accordingly:*

Eligible subjects who enter directly into SP848 (without prior participation in SP847 or another applicable LCM primary study) will initiate treatment with LCM at TV1, and the LCM dose will be titrated over the following week(s). Titration Visits are not applicable for subjects who have participated in SP847 or another LCM primary study; the first visit in SP848 for these subjects is Visit 1 (see Section 5.3).

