5. For subject who did not complete a C-SSRS at Screening, subject had actual suicidal ideation in the past 6 months as indicated by a positive response ("Yes") to either Question 4 or Question 5 of the screening version of the C-SSRS. The investigator must immediately refer the subject to a Mental Healthcare Professional and use clinical judgment as to whether to withdraw the patient from the study.

*Was revised as follows:*

All subjects discontinuing treatment with study medication for any reason should taper off medication as described in Section 4.4.1. Whenever possible, these cases should be discussed with the medical monitor prior to withdrawing the subject from the study. All subjects who withdraw from the study due to an AE must be followed until resolution of the event or until the event is considered stable. The following criteria for subject withdrawal from SP848 are outlined below. Additional discontinuation criteria for potential drug-induced liver injury are presented in Section 4.3.3.1.

Participation in this study **must** be discontinued for any of the following reasons:

1. Intolerable AEs, including clinically relevant abnormal laboratory findings that, in the opinion of the investigator, preclude further participation in the study
2. The request of the Sponsor or a Regulatory Agency

3. Subject achieves menarche during the study and does not practice an acceptable method of contraception for the duration of the study (unless sexually abstinent).
4. Subject becomes pregnant, as evidenced by a positive pregnancy test.
5. Subject has a corrected QT interval (QTc) of greater than or equal to 500ms as confirmed by a cardiologist overread on any ECG.
6. Subject develops a second-degree atrioventricular (AV) block while awake or develops a third-degree AV block at any time.
7. Subject is unwilling or unable to continue, or the caregiver/parent/legal guardian is unwilling or unable to allow the subject to continue in the study.
8. Investigator's decision that withdrawal from further participation would be in the subject's best interest.
9. Subject experiences convulsive status epilepticus (if none had occurred prior to study entry) and is compliant with study treatment

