An AE or laboratory value (as defined below) suggestive of internal organ involvement (including but not limited to hepatitis, nephritis, pneumonitis, carditis, colitis, encephalitis, pancreatitis, myositis, arthritis, or hematologic system involvement) combined with at least one of the following: fever, rash, lymphadenopathy, or eosinophilia.

Treatment-emergent abnormal laboratory value criteria suggestive of internal organ involvement or eosinophilia:

- Eosinophils %  $\geq 10\%$
- Eosinophils absolute  $\geq 0.5\text{G/L}$
- Neutrophils absolute  $<1.5\text{G/L}$
- Platelets  $\leq 100\text{G/L}$
- ALT  $\geq 2\text{x ULN}$
- AST  $\geq 2\text{x ULN}$

*Was revised as follows:*

An AE of special interest is any AE that a regulatory authority has mandated to be reported on an expedited basis, regardless of the seriousness, expectedness, or relatedness of the AE to the administration of a UCB product/compound.

The following are the LCM AEs of special interest:

- The following arrhythmias: atrial fibrillation/flutter, ventricular tachycardia or fibrillation, AV block (second degree Type I and II and third degree), and marked bradycardia (<45beats/min)
- Syncope or loss of consciousness (other than seizure related)
- Serious suspected multiorgan hypersensitivity reactions

Serious suspected multiorgan hypersensitivity cases may be identified and reported to the sponsor by the investigator using the following algorithm as agreed with the Food and Drug Administration:

An AE or laboratory value (as defined below) suggestive of internal organ involvement (including but not limited to hepatitis, nephritis, pneumonitis, carditis, colitis, encephalitis, pancreatitis, myositis, arthritis, or hematologic system involvement) combined with at least one of the following: fever, rash, lymphadenopathy, or eosinophilia.

Treatment-emergent abnormal laboratory value criteria suggestive of internal organ involvement or eosinophilia:

- Eosinophils %  $\geq$ 10%
- Eosinophils absolute  $\geq$ 0.5G/L
- Neutrophils absolute  $<$ 1.5G/L
- Platelets  $\leq$ 100G/L
- ALT  $\geq$ 2x ULN
- AST  $\geq$ 2x ULN

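### Direct enrollers are screened on QT (>450 ms) but must be withdrawn on QTc (≥500 ms), so at faster heart rates the written entry rule can pass a child who already meets the withdrawal limit

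*Protocol*

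**What the plan says.** Section 4.3.2 of the protocol, as revised in Amendment 4 (Section 17.4), has a block of criteria for the direct-enrolment group only: "Subjects who enroll directly into SP848 without previous participation in a LCM clinical study are not permitted to enroll" if any of them is met. Criterion 10 in that block begins "Subject has a clinically relevant ECG abnormality, in the opinion of the principal investigator" and then specifies, after an ie, "second or third degree heart block at rest or a QT prolongation greater than 450ms". No rate correction is mentioned.

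Section 4.3.3, as revised in Amendment 6 (Section 17.6), lists among the mandatory reasons for withdrawal, as criterion 5: "Subject has a corrected QT interval (QTc) of greater than or equal to 500ms as confirmed by a cardiologist overread on any ECG".

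The Screening Visit (Section 5.1) requires a "12-lead ECG (2 interpretable recordings approximately 20 to 30 minutes apart prior to vital signs assessment and collection of blood sample", and ECGs recur at every Titration Visit (Section 5.2). The only heart-rate figure in the text available is the adverse event of special interest "marked bradycardia (<45beats/min" in Section 8.2.2. No correction formula and no normal paediatric heart-rate range appear there.

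The amendment log shows no later change to exclusion criterion 10. Amendment 5 alters exclusion criterion 3. Amendment 6 alters criteria 2 and 9, removes the vigabatrin and felbamate criterion, rewords the one on monoamine oxidase inhibitors, and adds the liver and EP0060 criteria. Amendment 7 only renumbers. Amendment 8 lists no change to Section 4.3.2.

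**The concern.** QT shortens as heart rate rises, and QTc is intended to remove that dependence. A fixed QT limit is therefore lenient on the QTc scale at fast rates and strict at slow ones. Read as numbers, 450 at entry and 500 at withdrawal look like a 50 ms margin. That margin exists only if both refer to the same quantity.

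As written, a child could satisfy the entry limit on an ECG whose corrected value already requires withdrawal. Such a child would be enrolled, perhaps dosed, and then withdrawn at the first cardiologist overread for something present at Screening. How strict the entry rule is would also vary with heart rate, and so probably with age across the 4 to 17 range.

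The group concerned is not small. It is approximately 100 direct enrollers at selected sites, with about 46 named for Japan and 60 for China, in a study of up to approximately 400. The total is at most about 206 (100 + 46 + 60) if all three figures add, which the text does not make fully clear.

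**Working it through.** The plan gives no figure of its own to reproduce here. The check asks which QTc values are compatible with passing the entry limit.

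**Inputs from the protocol.** The longest QT not excluded is 450 ms (exclusion criterion 10). Withdrawal is required at a QTc of 500 ms or more (withdrawal criterion 5).

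**Assumptions.** The correction formula is not stated in the text available, so four common ones are used. Heart rate is recorded as part of "Vital signs assessment (blood pressure and pulse") but no range is given, so 50 to 120 beats/min is shown as an illustration.

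**Formulas**, with RR = 60/HR in seconds:
- Bazett: QTc = QT / RR^(1/2)
- Fridericia: QTc = QT / RR^(1/3)
- Hodges: QTc = QT + 1.75 × (HR − 60)
- Framingham: QTc = QT + 154 × (1 − RR)

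**Step 1. Heart rate at which QT 450 ms becomes QTc 500 ms.**
- Bazett: RR = (450/500)² = 0.81 s, so HR = 60/0.81 = 74.1
- Fridericia: RR = (450/500)³ = 0.729 s, so HR = 60/0.729 = 82.3
- Hodges: HR = 60 + 50/1.75 = 88.6
- Framingham: RR = 1 − 50/154 = 0.675 s, so HR = 60/0.675 = 88.9

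**Step 2. QTc (ms) when QT is 450 ms.**

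| HR | Bazett | Fridericia | Hodges | Framingham |
|---|---|---|---|---|
| 50 | 410.8 | 423.5 | 432.5 | 419.2 |
| 60 | 450.0 | 450.0 | 450.0 | 450.0 |
| 80 | 519.6 | 495.3 | 485.0 | 488.5 |
| 90 | 551.1 | 515.1 | 502.5 | 501.3 |
| 100 | 580.9 | 533.5 | 520.0 | 511.6 |
| 120 | 636.4 | 567.0 | 555.0 | 527.0 |

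At 80 beats/min only Bazett puts the child over 500 ms. At 90 and above all four do.

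**Step 3. Shortest QT (ms) that already gives QTc 500 ms.**

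| HR | Bazett | Fridericia | Hodges | Framingham |
|---|---|---|---|---|
| 90 | 408.2 | 436.8 | 447.5 | 448.7 |
| 100 | 387.3 | 421.7 | 430.0 | 438.4 |
| 120 | 353.6 | 396.9 | 395.0 | 423.0 |

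Every entry is below 450 ms. The eligible but must-withdraw band therefore runs from the tabulated value up to 450 ms. At 90 beats/min it is about 42 ms wide under Bazett (450 − 408.2) and about 1 ms under Framingham (450 − 448.7). At 100 beats/min it is about 63 ms (450 − 387.3) and 12 ms (450 − 438.4).

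**Step 4. The slow-rate direction.** At 50 beats/min a QT just over 450 ms is excluded, although the corrected value is about 411 ms (Bazett) to 433 ms (Hodges).

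**Step 5. Source of the overlap.** If both existing numbers referred to one quantity, the overlap would vanish at every heart rate, since 450 is below 500. The misfire comes wholly from the two scales. This says nothing about which measure or limit is clinically right.

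**The case against.** The strongest reply is that QT prolongation with a 450 ms limit may simply be loose wording for QTc. Nothing in the text contrasts the two terms deliberately, and each rule uses its term in a single criterion. That may be so, but the withdrawal rule spells out "corrected QT interval (QTc") and the entry rule does not. Sites apply what is written, and if shorthand was meant the correction is trivial.

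Second, there are safeguards. Criterion 10 invokes the principal investigator's opinion, exclusion criterion 5 lets the investigator refuse any child whose medical condition could jeopardise participation, other criteria cover significant heart disease, treated arrhythmia and sodium channelopathy, and withdrawal needs cardiologist confirmation. The grossest values in the tables would probably be noticed. This partly stands. Criterion 10 narrows its own opinion clause by listing what counts after an ie, but exclusion criterion 5 is not narrowed. Discretion lessens the practical effect without putting the two limits on one scale.

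Third, a reader might infer that a pre-existing long QTc would be counted as arising on lacosamide. The documents do not support that. Section 12.1.2.1.1 counts an event as treatment-emergent only if it starts or worsens on or after the first dose in this study, the primary withdrawal variable in Section 4.2.1.1 is restricted to such events, and Baseline for direct enrollers is the Screening Visit (Sections 12.1 and 12.1.2.2). An abnormality already present and not worsening falls outside these definitions. What remains is the chance that the withdrawal itself is misread.

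Fourth, it is tempting to say that the overlap occurs at ordinary paediatric heart rates, or to fault the absent formula. The text available gives no heart-rate range, and the formula may stand in the first part of the protocol or in the SAP. Neither is claimed here.

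**Conclusion.** The point holds as an inconsistency between two stated thresholds. For direct enrollers, the written entry limit permits a child whose QTc already meets the mandatory withdrawal limit once heart rate exceeds about 74 (Bazett), 82 (Fridericia) or 89 (Hodges, Framingham) beats/min. At slow rates it excludes children with an unremarkable QTc.

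Its reach is limited. Only children with a long QT for their rate are affected, and their number is unknown. Roll-over subjects come under exclusion criterion 2 instead. The study is single-arm and descriptive, and no primary estimate is shown to be distorted.

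The conclusion rests on three things: QT in criterion 10 means uncorrected QT; heart rates above these crossovers occur at Screening; and the Amendment 4 wording is still current. The last is inferred from the amendment log, because the consolidated Section 4.3.2 and the local amendments for Japan and China (5.2 and 5.4) are not available.

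**What to change.** The sponsor should reconcile exclusion criterion 10 (Section 4.3.2) with withdrawal criterion 5 (Section 4.3.3). It should be clear whether both refer to the same QT measure, and a child who passes entry should not be able to meet the mandatory withdrawal limit already. The choice of measure, correction formula and limits is the sponsor's; none is proposed here.

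In the analysis, add one descriptive listing of direct enrollers whose Screening QTc already met the withdrawal limit, where it can be derived from the recorded ECG data. A withdrawal that follows would then not be read as emerging on lacosamide.

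The cost is a wording change, one listing, and possibly a few more screen failures, depending on how the sponsor resolves the entry limit.

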### Recommended LCM dose reduction (taper) for oral solution (syrup) formulation

Maximum LCM dose achieved a	Taper schedule		
	Week 1	Week 2	Week 3
12mg/kg/day (6mg/kg bid)	8mg/kg/day (4mg/kg bid)	4mg/kg/day (2mg/kg bid)	0
10mg/kg/day (5mg/kg bid)	6mg/kg/day (3mg/kg bid)	2mg/kg/day (1mg/kg bid)	0
8mg/kg/day (4mg/kg bid)	4mg/kg/day (2mg/kg bid)	0	–
6mg/kg/day (3mg/kg bid)	2mg/kg/day (1mg/kg bid)	0	–
4mg/kg/day (2mg/kg bid)	0	–	–

bid=twice daily; LCM=lacosamide

a Maximum LCM dose achieved is based upon the maximum recommended dose in SP847.

### Recommended LCM dose reduction (taper) for tablet formulation

Maximum LCM dose achieved a	Taper schedule		
	Week 1	Week 2	Week 3
600mg/day (300mg bid)	400mg/day (200mg bid)	200mg/day (100mg bid)	0
500mg/day (250mg bid)	300mg/day (150mg bid)	100mg/day (50mg bid)	0
400mg/day (200mg bid)	200mg/day (100mg bid)	0	–
300mg/day (150mg bid)	100mg/day (50mg bid)	0	–
200mg/day (100mg bid)	0	–	–

bid=twice daily; LCM=lacosamide

a Maximum LCM dose achieved is based upon the maximum recommended dose in SP847.

*Was revised as follows (including additions of subsection headings 4.4.1.1 [Subjects enrolling from SP847 or other LCM pediatric clinical studies in epilepsy], 4.4.1.2 [Subjects enrolling directly in SP848], 4.4.1.3 [All subjects], and 4.4.1.4 [Study completion]):*

Subjects who have participated in SP847 (or other LCM pediatric clinical studies in epilepsy), who are eligible to participate in the open-label study SP848, and who choose to enter SP848, will begin SP848 on the LCM dose they achieved in the primary study.

Beginning with Protocol Amendment 4, at selected sites, up to approximately 100 eligible pediatric subjects  $\geq 4$  years to  $\leq 17$  years of age who have not previously participated in a LCM clinical study will be permitted to enroll directly into SP848. After Screening, eligible subjects will initiate treatment with LCM (oral solution or tablet, as chosen by the investigator and subject/caregiver), and the LCM dose will be titrated to a level to optimize tolerability and seizure control.

At the first Titration Visit (TV) (see Section 5.2), subjects who have enrolled directly into SP848 will receive a single dose of LCM (1mg/kg [oral solution] or 50mg [tablet]) during the clinic visit. Over the following days, subjects will be administered LCM 1mg/kg bid (oral solution) or LCM 50mg bid (tablet), and will begin titrating in weekly increments of 2mg/kg/day (oral solution) or 100mg/day (tablet) up to a level to optimize tolerability and seizure control (not to exceed 12mg/kg/day [or 600mg/day based on body weight, whichever is lower]). Subjects must be on each LCM dose for at least 5 days before titrating up to the next dose.

A total of up to 6 Titration Visits may be required (eg, for a subject whose dose is titrated to the maximum permitted dose of LCM 12mg/kg/day). However, based on tolerability and seizure control, a subject's LCM dose may be titrated to a lower dose level; in such a case, fewer than 6 Titration Visits would be required.

The following table summarizes the recommended titration steps for the oral solution and tablet formulations:

### **Recommended LCM dose titration for subjects enrolling directly into SP848**

Formulation	Week 1	Week 2	Week 3	Week 4	Week 5	Week 6
Oral solution (syrup)	2mg/kg/day (1mg/kg bid)	4mg/kg/day (2mg/kg bid)	6mg/kg/day (3mg/kg bid)	8mg/kg/day (4mg/kg bid)	10mg/kg/day (5mg/kg bid)	12mg/kg/day (6mg/kg bid)
Tablet	100mg/day (50mg bid)	200mg/day (100mg bid)	300mg/day (150mg bid)	400mg/day (200mg bid)	500mg/day (250mg bid)	600mg/day (300mg bid)

bid=twice daily; LCM=lacosamide

The investigator, together with the subject/caregiver (including parent/legal guardian), will be able to choose either the oral solution (syrup) formulation or the tablet formulation of LCM in this study. The study medication will be orally administered bid (at 12-hour intervals, once in the morning and once in the evening) in equally divided doses. The oral solution (syrup) formulation will be measured and orally administered via a dosing syringe. The selection of doses, titration

scheme, and rate of taper in SP847 were based on adult studies and were adjusted to a mg/kg basis plus 40% (ie, 600mg/day adult dose of LCM corresponds to [600mg/70kg] x 1.4 = approximately 12mg/kg/day for a child). The selection of doses in this trial is based on the maximum recommended dose in SP847.

The investigator may adjust the LCM dose to a minimum of 2mg/kg/day (oral solution [syrup]) or 100mg/day (tablet) and a maximum of 12mg/kg/day (oral solution [syrup]) or the corresponding dose levels for the tablet formulation) not to exceed 600mg/day based on body weight, even if the subject's body weight exceeds 50kg. The maximum permitted LCM dose in SP848 is 12mg/kg/day or 600mg/day, whichever is lower.

The investigator may increase the dose of LCM no faster than 2mg/kg/day (oral solution [syrup]) or 100mg/day (tablet) per week to a maximum of 12mg/kg/day (oral solution [syrup]) or the corresponding dose levels for the tablet formulation) not to exceed 600mg/day based on body weight, even if the subject's body weight exceeds 50kg. The maximum permitted LCM dose in SP848 is 12mg/kg/day or 600mg/day, whichever is lower. The investigator may decrease the dose of LCM to a minimum of 2mg/kg/day (oral solution [syrup]) or the corresponding dose level for the tablet formulation). Increases in the LCM dose must occur only during office visits. It should be noted, in cases of incomplete doses (eg, subject spits out all or a portion of the syrup), missed doses, or administration of an erroneous volume of syrup, study medication should not be readministered and these subjects would remain at their assigned dose.

Subjects enrolling from SP847 will have the option of remaining on the oral solution formulation of LCM or switching to the commercial tablet formulation, if feasible. Consideration of the current LCM milligram dose in the oral solution (syrup) should occur if/when transitioning to the tablet formulation. In cases where the LCM dose received with the oral solution (syrup) is not supported by the tablet strengths available in SP848 (50mg and 100mg), a clinical decision must be made by the investigator or other study physician to either increase or decrease the LCM dose to the next multiple of 100mg with a maximum permitted dose of 600mg/day.

Subjects achieving a dose of LCM  $\geq$ 6mg/kg/day (oral solution [syrup]) or  $\geq$ 300mg/day (tablet) who withdraw during the study should taper off study medication. It is recommended that the dose be tapered gradually in weekly decrements of 4mg/kg/day (oral solution [syrup]) or 200mg/day (tablet) (see tables below). A slower taper of 2mg/kg/day (oral solution [syrup]) or 100mg/day (tablet) is permitted, if medically necessary. In case of an emergency, a faster taper is permitted after discussion with the medical monitor, whenever possible.

